4.2.2 Rationale for the Use of Comparator/Placebo

A placebo-controlled study will minimize bias during assessment of safety, tolerability, and immunogenicity. In addition, placebo serves as a negative control for potential environmental exposures to SARS-CoV-2 and provides a control for immunologic assays.

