As participants in Panel A, Panel B, and the first 5 subjects in Panel E will be amongst the first to receive doses of $1 \cdot 10^5$ TCID₅₀, $1 \cdot 10^6$ TCID₅₀, and $1 \cdot 10^7$ TCID₅₀ V591 respectively, they will be required to be seronegative for SARS-CoV-2 as an additional precaution. Participants in the rest of the study will not be screened by serology for SARS-CoV-2 and thus will not be required to be seronegative for enrollment.

Doses of $1 \cdot 10^5$ TCID₅₀ and $1 \cdot 10^6$ TCID₅₀ will also be the only dose levels administered to older participants after they have been assessed to be well tolerated in younger adults based on data from this study or the COVID-19-101 study as outlined in Section 4.1. These are doses that are most likely to be both well tolerated and immunogenic in this population, and it is intended to only administer V591 doses that are generally well tolerated and anticipated to elicit an immune response against SARS-CoV-2 in older participants. Two dose regimens of V591 will be given either 8 or 24 weeks apart in Panels of adults > 55 years of age. As older adults have historically demonstrated weaker responses to vaccines [Weinberger, B. 2012], 2 dose regimens of V591 with wider intervals than the 4 week interval in the COVID-19-101 study will be evaluated in an effort to identify a regimen of V591 that displays enhanced immunogenicity in older adults. This design will minimize the risks to older participants while efficiently obtaining immunogenicity data in this older population that is at greatest risk for severe COVID-19 disease.

In an previous Phase 1 study, MV-CHIK 101, that explored doses ranging from $1.5 \cdot 10^4$ to $3 \cdot 10^5$ TCID₅₀ of MV-CHIK in healthy adults, Doses of $7.5 \cdot 10^4$ and $3 \cdot 10^5$ TCID₅₀ MV-CHIK were generally immunogenic after a single vaccination, while the lower dose of $1.5 \cdot 10^4$ TCID₅₀ required 2 doses for comparable immunogenicity. Based on this clinical data, it is anticipated that a single dose of V591 greater than $7.5 \cdot 10^4$ TCID₅₀ may provide adequate immunogenicity after a single dose. Thus a single dose of $1 \cdot 10^5$ TCID₅₀ will be the lowest dose administered as a single dose regimen in this trial.

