9.6.2 Statistical Methods for Immunogenicity Analyses

This section describes the statistical methods that address the secondary immunogenicity objectives. Methods related to exploratory objectives will be further described in the supplemental statistical analysis plan.

The geometric mean ratios and 95% CIs of the anti-SARS-CoV-2 spike serum nAb GMTs will be calculated using a cLDA method proposed by Liang and Zeger (2000) [Liang, K-Y and Zeger, S. L. 2000]. In this model, the response vector consists of the log-transformed prevaccination and postvaccination antibody titers. The repeated measures model will include terms for time, the interaction of time-by-vaccination group (with a restriction of the same baseline mean across groups). The treatment difference in terms of a geometric mean ratio at a given postvaccination time point will be estimated and tested from this model. The term for time will be treated as a categorical variable. An unstructured covariance matrix will be used to model the correlation among repeated measurements. This model allows the inclusion of participants who are missing either the baseline or postbaseline measurements, thereby increasing efficiency.

The observed nAb GMTs at each timepoint with serum collection and GMFRs from prevaccination to postvaccination will be performed within each vaccination group separately. Descriptive statistics with point estimates and within-group 95% CIs will be provided. The point estimates will be calculated by exponentiating the estimates of the mean of the natural log values and the within-group CIs will be derived by exponentiating the bounds of CIs of the mean of the natural log values based on the t-distribution.

A similar statistical approach will be used to evaluate the anti-SARS-CoV-2 spike serum IgG responses.

For responses smaller than the lower limit of quantitation (LLOQ), half of the LLOQ will be used for analysis when calculating the nAb GMTs and IgG GMCs.

A detailed analysis strategy for key immunogenicity endpoints is listed in [Table 10](#).

Table 10 Analysis Strategy for Immunogenicity Variables

Endpoint/Variable (Description, Time Point)	Primary vs. Supportive Approach ^a	Statistical Method	Analysis Population	Missing Data Approach
Secondary Endpoint				
nAb GMT ratio and IgG GMC ratio at Day 29 (all panels) and Day 85 (2-dose panels only)	P/S	cLDA model ^b (estimate and 95% CI)	PP/FAS	Model-based

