nAb GMT and IgG GMC at all timepoint with serum collection	P	Descriptive Statistics (estimate, 95% CI)	PP	Missing data will not be imputed
GMFR from baseline to postvaccination for nAb and IgG	P	Descriptive Statistics (estimate, 95% CI)	PP	Missing data will not be imputed
CI = confidence interval; FAS = Full Analysis Set; GMC = geometric mean concentration; GMFR=geometric mean foldrise; GMT = geometric mean titer; IgG = Immunoglobulin G; nAb = neutralizing antibody; PP = Per-Protocol. ^a P = Primary approach; S = Supportive approach. ^b Estimation of the GMT ratios and computation of the corresponding 95% CIs will be calculated using t-distribution with the variance estimate from a constraint longitudinal data model (cLDA) utilizing the log-transformed antibody titers as the response and a single term for vaccination group.				

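### The titre-ratio model gives placebo and every V591 group the same covariance matrix, so its 95% intervals are likely to have the wrong width, and Table 10 footnote b describes a different model

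*Combined protocol and SAP*

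**What the plan says.** Section 9.6.2 states the method: "The geometric mean ratios and 95% CIs of the anti-SARS-CoV-2 spike serum nAb GMTs will be calculated using a cLDA method". The terms are time (categorical) and time by vaccination group, "with a restriction of the same baseline mean across groups". On covariance it says only: "An unstructured covariance matrix will be used to model the correlation among repeated measurements". It gives no group-specific covariance, robust standard error or fallback structure. It does not say which visits enter a fit, or whether a vaccination group is a dose level, a regimen or a panel.

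For results below the LLOQ, "half of the LLOQ will be used for analysis when calculating the nAb GMTs and IgG GMCs". Section 4.2.2 says that "placebo serves as a negative control for potential environmental exposures to SARS-CoV-2". Section 4.2.6 adds that, outside the sentinels, "Participants in the rest of the study will not be screened by serology for SARS-CoV-2".

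Table 10 asks for model-based ratios at Day 29 and Day 85. Its footnote b describes the model as "utilizing the log-transformed antibody titers as the response and a single term for vaccination group".

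**The concern.** A single covariance matrix gives all groups the same variance at each visit. A negative-control arm with most values replaced by one constant has little spread, while a vaccinated arm has much more. Group sizes also differ, from about 17 to 71 evaluable per dose level against 44 on placebo. Under those conditions a pooled variance does not give a 95% interval its nominal coverage. The error can go either way, depending on the group's size and spread.

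The ratio and its interval are the key secondary comparison. The Amendment 04 text in Section 8.11.4 ends the study on immunogenicity results, so the Day 29 ratio carries most of the weight. Footnote b adds a second problem: the plan contains two different models for the same ratio.

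**Working it through.** **Inputs.**
- Tables 3 and 4 give 84 participants each on 10^5 and 10^6, 20 each on 10^4 and 10^7, and 52 on placebo.
- Section 9.9.2 assumes 85% evaluable at Day 29, which gives 71, 71, 17, 17 and 44.
- Table 13 uses log SDs of 1.0, 1.5 and 2.0. I take 1.0 for V591.
- The placebo SD s0 is my assumption, shown as a range.
- I read vaccination group as dose level, as in Table 12.

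**1. Table 13.** With one common SD, the interval is ratio × exp(± t × SD × √(1/n1 + 1/n0)). Take n1 = 71, n0 = 48 (57 × 0.85, the placebo count in Section 9.9.2) and t = 1.980 on 117 df. For SD 1.0 and ratio 1.5 the half-width is 1.980 × √(1/71 + 1/48) = 0.370, giving (1.04, 2.17) as printed. The same formula reproduces all 24 bounds, so the plan's precision table also assumes equal spread in both arms. The design has 52 placebo participants, so I use 44 below.

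**2. Equal V591 SDs, five groups.**
- Pooled variance = (172 × 1.0² + 43 × s0²)/215, where 172 = 16 + 70 + 70 + 16.
- Pooled SE = √(pooled variance × (1/n + 1/44)).
- True SE = √(1.0²/n + s0²/44).
- Coverage ≈ P(|Z| < 1.96 × SE ratio).

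| s0 | Pooled variance | Pooled SE, n = 71 | True SE | SE ratio | Coverage |
|---|---|---|---|---|---|
| 0 | 0.800 | 0.172 | 0.119 | 1.45 | 99.5% |
| 0.25 | 0.8125 | 0.173 | 0.125 | 1.39 | 99.4% |
| 0.5 | 0.850 | 0.177 | 0.141 | 1.26 | 98.6% |
| 0.65 | 0.884 | 0.180 | 0.154 | 1.17 | 97.8% |
| 0.8 | 0.928 | 0.185 | 0.169 | 1.09 | 96.8% |

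For a ratio of 2.0 and s0 = 0.25, 2 × exp(± 1.96 × SE) is (1.43, 2.81) with the pooled SE and (1.57, 2.55) with the true SE.

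For n = 17 and s0 = 0, 0.25 or 0.5, the SE ratio is 1.05, 1.05 or 1.04.

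**3. Check with the longitudinal model.** In 4,000 simulated fits on Days 1, 15, 29 and 85:
- For groups of 71, coverage was 99.3% to 99.5% at s0 = 0.05 or 0.25 and 98.6% to 99.1% at s0 = 0.5. The SE was 1.25 to 1.44 times the true value.
- For groups of 17, coverage was 95.6% to 96.3% and the SE ratio 1.03 to 1.05.
- With equal SDs in all arms, coverage was 94% to 95%.

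**4. How large could s0 be?** Suppose 2 of 44 placebo participants had undetected prior infection, with titres 10, 20 or 50 times LLOQ/2, and the rest sit at LLOQ/2. Then s0 = ln(fold) × √((2 × 42/44)/43) = 0.49, 0.63 or 0.82. This is the reason for the last two rows of the table.

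**5. Spread that differs by dose.** Take illustrative SDs of 0.3, 0.8, 1.0 and 1.5 for 10^4 to 10^7, and 0.25 for placebo.
- Pooled variance = (16 × 0.09 + 70 × 0.64 + 70 × 1 + 16 × 2.25 + 43 × 0.0625)/215 = 0.721.
- For 10^7, pooled SE = √(0.721 × (1/17 + 1/44)) = 0.242 and true SE = √(2.25/17 + 0.0625/44) = 0.366.
- The ratio is 0.66 and coverage about 80%.
- Separating only placebo from all V591 leaves 10^7 at about 79%. A variance for each group restores 95%.

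**6. Visits.** The serum days are:
- 1-dose panels: 1, 15, 29, 57, 85, 115, 211, 365.
- Day 1/57 panels: 1, 15, 29, 57, 71, 85, 115, 211, 422.
- Day 1/169 panels: 1, 15, 29, 85, 169, 197, 365, 534.

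The union has 13 days and 13 × 12/2 = 78 pairs. The schedules contain 28, 36 and 28 pairs. Their overlaps contain 21, 10 and 6, with 6 common to all three. So 28 + 36 + 28 − 21 − 10 − 6 + 6 = 61 pairs are observed together and 17 never are (for example 71/197 and 422/534). In a simulated data set, a 13-visit fit reached the same likelihood from three starting points with different values for those covariances. The Day 29 log ratio and SE (0.639, 0.123) did not change, and they equalled the fit on Days 1, 15, 29 and 85 alone. A baseline that is constant at LLOQ/2 made the matrix singular.

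**7. Footnote b.** Time-by-group terms give a separate ratio at each visit. One group term gives the same ratio at every visit, yet Table 10 asks for Day 29 and Day 85 separately.

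**The case against.** The size of the problem rests on an assumed placebo SD. Nothing in the documents says that placebo will all fall below the LLOQ, and unscreened participants may include seropositives, which shrinks the excess width. That stands, and the range above reflects it. The study is descriptive, most of the errors are conservative, and each group's own t-based interval is reported, so unequal spread would be visible. That also stands, and it limits the severity.

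The grouping matters too. If each panel is its own group compared with pooled placebo, every main group has about 17 evaluable participants. With equal V591 SDs the pooled interval is then nearly right (SE ratio 1.03 at s0 = 0.5).

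Two stronger readings are tempting and are not supported:
- A reader might infer that the schedules do not overlap and the model cannot be estimated. Days 1, 15, 29 and 85 are common to all three schedules, both Table 10 comparison days are among them, and no section calls for a 13-visit fit.
- A reader might infer coverage near 80% for any small dose group, or intervals about 1.8 times too wide. With equal V591 SDs these need, respectively, a separate two-group fit of 17 versus 44 or all V591 pooled against placebo (177 versus 44). Section 9.6.2 describes neither.

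**Conclusion.** The concern holds in a limited form. Under a five-group fit with V591 log SD 1.0, the Day 29 intervals for 10^5 and 10^6 are about 1.25 to 1.45 times too wide on the log scale if the placebo SD is 0 to 0.5, and 1.09 to 1.17 times if it is 0.65 to 0.8. Intervals for groups of 17 are nearly right when the V591 groups share one SD. They can be too narrow (about 80% coverage) for a dose with much larger spread than the rest. All SDs here are assumptions; the documents give none for placebo and none by dose.

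The conflict between footnote b and the text needs no assumption. The unidentified covariances matter only if all 13 visits enter one fit, and they do not affect the Day 29 ratio. The plan should be corrected before the final analysis, but the issue does not undermine the study's primary safety objective.

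**What to change.** In Section 9.6.2 and the matching row of Section 9.1:
- Define vaccination group, and list the panels and visits in each fit. Use the visits shared by the panels compared (Days 1, 15, 29 and 85), and within-schedule visits for any later comparison such as Day 197 in Section 3.
- Estimate a separate covariance matrix for each vaccination group, not merely placebo against all V591, with Satterthwaite or Kenward-Roger degrees of freedom.
- If any group's matrix, including its baseline element, is singular because values sit at LLOQ/2, report the Welch interval on log titres at that visit. It remains defined when placebo has no spread.
- Rewrite footnote b to name time and time-by-vaccination-group terms.

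The cost is wording and a model option; no visit or sample changes. Four visits need 4 × 5/2 = 10 covariance parameters per group, so 50 in place of 10 for five groups. Variance estimates in groups of 17 become somewhat less stable. With V591 SD 1.0 and s0 = 0, their log half-width goes from 1.971 × 0.255 = 0.503 to 2.120 × 0.243 = 0.514, about 2% wider.

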Duration of Participation	Each participant will participate in the study for approximately 15 to 19 months for 2-dose panels and 13 months for 1-dose panels from the time the participant provides documented informed consent through the final contact. After a screening phase of 28 days, each participant will be receiving either 2 doses of assigned intervention (Panels A, B, F, I, J, K and L) or 1 dose of assigned intervention (Panels C-E and G-H). After the last vaccination, each participant will be followed for 12 months.
---------------------------	-----------------------------------------------------------------------------------------------------------------------------------------------------------------------------------------------------------------------------------------------------------------------------------------------------------------------------------------------------------------------------------------------------------------------------------------------------------------------------------------------------------------------

Study Governance Committees:

Steering Committee	No
Executive Oversight Committee	No
Data Monitoring Committee	Yes
Clinical Adjudication Committee	No
Insert Other Oversight Committee	No
Study governance considerations are outlined in Appendix 1.	

Study Accepts Healthy Volunteers: Yes

A list of abbreviations used in this document can be found in Appendix 10.

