3 HYPOTHESES, OBJECTIVES, AND ENDPOINTS

Healthy male participants and female participants between the ages of 18-55 years (inclusive) of age in Parts 1 and 2A (younger adults) and > 55 years of age in Part 2B (older adults)

Objectives	Endpoints
Primary	
To assess the safety and tolerability of V591 compared with placebo	
Solicited injection site adverse events from Day 1 through Day 5 after any study intervention
 
Solicited systemic adverse events from Day 1 through Day 14 after any study intervention
 
Unsolicited adverse events from Day 1 through Day 28 after any study intervention
 
SAEs from Day 1 throughout the duration of study
 
Medical attended AEs (MAAEs) collected from Day 1 throughout the duration of study

Secondary	
To compare the humoral immunogenicity of V591 with placebo at Day 29 (all panels) and Day 85 (Panels A, B, I, and J) or Day 197 (Panels K and L)	
Anti-SARS-CoV-2 spike serum neutralizing antibody (nAb) responses, as measured by Pseudo-virus Neutralization Assay (PNA)
 
Anti-SARS-CoV-2 spike Immunoglobulin G (IgG) responses, as measured by ELISA

To evaluate the humoral immunogenicity of V591 at all timepoints with serum collection	
Anti-SARS-CoV-2 spike serum nAb responses, as measured by Pseudo-virus Neutralization Assay (PNA)
 
Anti-SARS-CoV-2 spike IgG responses, as measured by ELISA

Tertiary/Exploratory	
To evaluate the immune response to of V591, including cell-mediated immunity	
PBMCs stimulated with SARS-CoV-2 Spike peptides for characterization of cell mediated immunity and serum to characterize the immune response to V591

[figure not shown]
Objectives	Endpoints
To characterize SARS-CoV-2 seroconversion rates among participants	Anti-SARS-CoV-2 N-protein IgG responses, as measured by immunoassay
To document confirmed diagnoses of SARS-CoV-2 infection among study participants	Laboratory confirmed diagnosis of SARS-CoV-2 infection reported as an ECI
To document study participants' exposures to confirmed SARS-CoV-2 cases	Known exposure to a confirmed case of active SARS-CoV-2 reported as an ECI

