4 STUDY DESIGN

4.1 Overall Design

This is a randomized, placebo-controlled, two-part, multi-site, double-blind dose-ranging study of V591 in healthy younger and older adults to be conducted in conformance with Good Clinical Practice in approximately 260 participants as outlined in [Figure 1](#).

Figure 1 Study Diagram

In this 2-part Phase 1/2 trial, two Sentinel Panels will be enrolled in Part 1 followed by the review of safety/tolerability data through 7 days following dose 1 by a standing internal Data Monitoring Committee (siDMC) prior to initiation of dosing in Parts 2A and 2B. The siDMC will also review the safety/tolerability data from the sentinel Panels through 7 days following dose 2 prior to administration of the 2nd dose in Panel F in Part 2A and Panels I-L in Part 2B. The study design is described in detail in the protocol text and the SoA.

In Part 1, approximately 10 healthy younger participants (age 18-55 years inclusive) will be enrolled in two Sentinel Panels, Panel A and Panel B, and administered two doses of either $1 \cdot 10^5$ TCID₅₀ or $1 \cdot 10^6$ TCID₅₀ V591. Five participants will be randomized into each Panel per dose to receive two vaccinations of V591 or placebo 56 days apart in a 4:1 ratio.

As safety precaution, the study will begin with the Day 1 vaccination of a small group of sentinel participants (5 participants from Panel A and 5 participants from Panel B) at one investigational site.

The first and the second participant of sentinel Panel A will receive the Day 1 vaccination on the same day, with an interval of at least 3 hours. Twenty-four hours after the injection, the participants will be called to collect safety information related to the vaccination. The clinical investigator can then decide to move on with the vaccination of the remaining 3 participants in Panel A based on the absence of related severe AEs/SAEs.

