The first and the second participant of sentinel Panel B may be enrolled at least seventy-two hours after the first participant in Panel A has received the first vaccination. The first and the second participant in Panel B will receive the Day 1 vaccination on the same day, with an interval of at least 3 hours. Twenty-four hours after the injection, the participants will be called to collect safety information related to the vaccination. The clinical investigator can then decide to move on with the vaccination of the remaining 3 participants in Panel B based on the absence of related severe AEs/SAEs.

In Part 2A, approximately 100 healthy younger participants (age 18-55 years inclusive) will be enrolled in four Panels, Panel C, Panel D, Panel E, and Panel F. Participants in Panels C-E will be administered a single dose of either $1 \cdot 10^5$ TCID₅₀, $1 \cdot 10^6$ TCID₅₀, or $1 \cdot 10^7$ TCID₅₀ of V591, respectively. Participant in Panel F will be administered 2 doses of V591 or placebo: $1 \cdot 10^4$ TCID₅₀ on Day 1 and $1 \cdot 10^5$ TCID₅₀ on Day 169. 25 participants will be randomized into each Panel per dose to receive a single vaccination of V591 or placebo in a 4:1 ratio. Part 2A may initiate based upon siDMC recommendation as outlined below and may initiate simultaneously with Part 2B. Panel C, Panel D, Panel E and Panel F may all be enrolled in parallel.

Panel E in Part 2A: As safety precaution, the enrollment for Panel E, the highest dose panel, will begin with the Day 1 vaccination with five sentinel participants at a single investigational site. The first 5 participants in Panel E will be enrolled and receive the Day 1 vaccination with an interval of at least 3 hours between each participant. Twenty-four hours after the injection, the participants will be called to collect safety information related to the vaccination. The clinical investigator can then decide to move on with the vaccination of the remaining participants in Panel E based on the absence of related severe AEs/SAEs.

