On Day 57 of the study, participants in the 2-dose Day 1, Day 57 panels (Panels A, B, I and J) will receive the second intramuscular injection of V591 or placebo into the deltoid muscle accordingly to protocol randomization schedule. Predose and post vaccination safety and immunogenicity assessments will be performed as set forth in the SoA. After injection, the participants will remain in the clinical sites for medical supervision and monitoring for a minimum of 8 hours after injection. (Panels A and B) and for a minimum of 1 hour after injection (Panels I and J).

Participant will be provided with a new VRC for the 28 following days. At the end of the visit, which lasts approximately 9 hours in Panels A and B , 2 hours for Panels I and J, once the study physician has determined that participant is fit to be released, the participant will be

discharged from the clinical site. The appointment for the phone call (24 hours \pm 6 hours) and for the next clinical visit will be scheduled and confirmed with the participant.

Day 169 (the second vaccination for 2-dose Day 1, Day 169 panels)

On Day 169 of the study participants in the 2-dose Day 1, Day 169 panels (Panels F, K and L) will receive the second intramuscular injection of V591 or placebo into the deltoid muscle accordingly to protocol randomization schedule. Predose and post vaccination safety and immunogenicity assessments will be performed as set forth in the SoA. After injection, the participants will remain in the clinical sites for medical supervision and monitoring for a minimum of 1 hour after injection.

Participant will be provided with a new VRC for the 28 following days. At the end of the visit, which lasts approximately 2 hours, once the study physician has determined that participant is fit to be released, the participant will be discharged from the clinical site. The appointment for the phone call (24 hours \pm 6 hours) and for the next clinical visit will be scheduled and confirmed with the participant.

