9.9.2 Sample Size and Power for Immunogenicity Analyses

This is a descriptive study and there are no hypotheses to be evaluated. This study will randomize approximately a total of 228 participants into 4 different dose-levels of the V591 group and 57 participants into the placebo group. Table 12 displays the numbers of participants scheduled to receive each study intervention.

Table 12 Numbers of Participants Scheduled to Receive Each Study Intervention

Treatment Group	Number of Participants		
	Day 1 (Dose 1 for all panels)	Day 57 (Dose 2 for Panels A, B, I, and J)	Day 169 (Dose 2 for Panels F [†] , K, and L)
V591-10 ⁴ /10 ⁵ TCID ₅₀	20	0	20
V591-10 ⁵ TCID ₅₀	84	24	20
V591-10 ⁶ TCID ₅₀	84	24	20
V591-10 ⁷ TCID ₅₀	20	0	0
125-fold dilution of V591-10 ⁷ TCID ₅₀	20	0	0
Placebo	57	12	15

TCID₅₀=median tissue culture infectious dose
[†]Participant in Panel F will be administered V591-10⁴ TCID₅₀ or placebo on Day 1, and V591-10⁵ TCID₅₀ or placebo on Day 169.

The width of the 95% CIs for the GMT/GMC ratios depend on the sample size, variability of the natural log concentrations, and the magnitude of the ratio. In Table 13, 95% CIs for various hypothetical GMT/GMC ratios at Day 29 and various hypothetical standard deviation estimates for the natural log titers are displayed. It is assumed that approximately 85% participants will be evaluable for immunogenicity analyses based on PP population at Day 29.

Table 13 95% CIs for Varying Hypothetical GMT/GMC Ratios (V591/Placebo) and Varying Standard Deviations

Standard Deviation of Natural Log Titers/Concentration	GMT/GMC Ratios (V591/Placebo)			
	1.5	2.0	2.5	3.0
1.0	(1.04, 2.17)	(1.38, 2.90)	(1.73, 3.62)	(2.07, 4.34)
1.5	(0.86, 2.61)	(1.15, 3.48)	(1.44, 4.36)	(1.72, 5.23)
2.0	(0.72, 3.14)	(0.95, 4.19)	(1.19, 5.24)	(1.43, 6.29)

CI=confidence interval; GMC=geometric mean concentration; GMT= geometric mean titer.

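### Table 10 sets the Day 85 antibody comparison for all two-dose panels and lists no Day 197 ratio, which conflicts with the panels and visits named in Section 3

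*Combined protocol and SAP*

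**What the plan says.** Section 3, and the synopsis in the same terms, set the placebo comparison at Day 29 for every panel and then at "Day 85 (Panels A, B, I, and J) or Day 197 (Panels K and L"). Panel F has no later comparison there.

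Section 9.6.2 presents Table 10 as the detailed strategy for the key immunogenicity endpoints. Its only between-group row reads "nAb GMT ratio and IgG GMC ratio at Day 29 (all panels) and Day 85 (2-dose panels only"). It names no panels and has no Day 197 entry.

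The synopsis uses the two-dose label for seven panels: "2 doses of assigned intervention (Panels A, B, F, I, J, K and L"). Dose 2 comes at two different times. Table 12 has "Day 57 (Dose 2 for Panels A, B, I, and J"), and Section 8.11.2 states that on Day 169 "participants in the 2-dose Day 1, Day 169 panels (Panels F, K and L) will receive the second intramuscular injection".

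On the model, the Section 9.6.2 text specifies a constrained longitudinal analysis (cLDA) with time and time-by-group terms and a common baseline. Footnote b to Table 10 describes the same analysis as "utilizing the log-transformed antibody titers as the response and a single term for vaccination group".

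**The concern.** Day 85 is 28 days after dose 2 in Panels A, B, I and J, but 84 days before dose 2 in F, K and L. Read literally, Table 10 puts both kinds of participant into the Day 85 comparison and leaves out the comparison Section 3 sets for K and L. A programmer working from Table 10 and one working from Section 3 would produce different tables. If the groups were also pooled by dose level, the Day 85 ratio would describe a mixture of one-dose and two-dose responses rather than the response to two doses.

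**Working it through.** **Step 1. Reproduce the plan's dose-2 counts.** Section 4.1 gives the panel sizes. For A and B, "Five participants will be randomized into each Panel per dose"; for Part 2A, "25 participants will be randomized into each Panel per dose", with the same number in each Part 2B panel. At 4:1, A and B have 4 V591 and 1 placebo each, and the others 20 and 5.

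- Dose 2 on Day 57 (A, B, I, J): V591 4 + 4 + 20 + 20 = 48; placebo 1 + 1 + 5 + 5 = 12.
- Dose 2 on Day 169 (F, K, L): V591 3 × 20 = 60; placebo 3 × 5 = 15.

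Table 12 gives 24 + 24 and 12, and 20 + 20 + 20 and 15. The counts agree.

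**Step 2. Who has had one dose at Day 85.**

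- All two-dose panels: V591 60 of 108, placebo 15 of 27, together 75/135 = 55.6%.
- 10^5 group: A 4 + I 20 + K 20 = 44, of whom K's 20 have had one dose; 20/44 = 45.5%.
- 10^6 group: B 4 + J 20 + L 20 = 44; again 20/44 = 45.5%.
- 10^4/10^5 group (Panel F): 20 of 20.

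**Step 3. Does another rule remove F, K and L?** No. The schedule in Section 1.3.3 draws serum for both assays from these panels on Day 85. The per-protocol exclusion in Section 9.5.2 applies to a second dose missed against the participant's own schedule, and theirs is not yet due. The Full Analysis Set needs only one vaccination and one serology result.

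**Step 4. How are vaccination groups formed?** The plan does not define the term for this model. Table 13 gives a hint. Its intervals follow ratio × exp(± t × SD × √(1/n1 + 1/n2)), with t the 97.5% point on n1 + n2 − 2 degrees of freedom and 85% of participants evaluable. With 84 V591 (one dose level over all its panels, Table 12) and 57 placebo, the evaluable numbers are 71 and 48. All 12 cells are then reproduced; for ratio 1.5 and SD 1.0 the interval is (1.04, 2.17). With 228 and 57 that cell would be (1.09, 2.06). So Table 13 pools panels by dose level. It concerns Day 29, however, when everyone has had one dose. The 57 placebo recipients in Table 12 exceed the 52 that the twelve panels supply; this is a separate matter and does not affect the dose-2 counts.

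**Step 5. Dilution if that pooling is carried to Day 85.** Pooled ratio = exp[(24/44) ln R2 + (20/44) ln R1], where R2 and R1 are the two-dose and one-dose ratios to placebo. The documents give no expected values, so Table 13's hypothetical ratios are used as assumptions.

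| R2 | R1 | Pooled ratio |
|---|---|---|
| 3.0 | 1.5 | 2.19 |
| 3.0 | 2.0 | 2.50 |

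This assumes the same placebo level in all panels, equal evaluability and head-count weights.

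**Step 6. Precision.** The formula of Step 4 is used with a ratio of 2.0. The 85% evaluable share is stated for Day 29 only and is carried forward here as an assumption.

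| Comparison at one dose level | Randomized | SD 1.0 | SD 2.0 |
|---|---|---|---|
| Day 85, all two-dose panels | 44 vs 27 | (1.18, 3.40) | (0.69, 5.79) |
| Day 85, A, B, I, J only | 24 vs 12 | (0.90, 4.42) | (0.41, 9.78) |
| Day 197, K or L | 20 vs 10 | (0.84, 4.76) | (0.35, 11.35) |

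The pooled estimate would look more precise than the comparison that Section 3 asks for.

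**The case against.** The best defence is that this is a slip of the pen. Section 9.3 sends the reader back to Section 3 for objectives, and Section 8.3.5 applies the two-dose label to Day 85 and Day 197 together, so Table 10 may simply have lost its Day 197 phrase. That is plausible, but restoring the phrase without panel names would not settle the matter, because F, K and L have serum at both visits.

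Several stronger readings are tempting, and the documents do not support them.

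- A reader might infer that the Day 197 objective has no analysis. The Section 9.6.2 text allows a cLDA ratio at any post-vaccination visit, Table 10 has descriptive estimates at every serum visit, and Section 9.7 permits a Day 197 interim analysis for K and L. What is missing is a listed ratio with its population and its primary or supportive role.
- A reader might infer that Table 10 pools boosted and unboosted participants. It states no pooling. Section 9.5.2 analyses participants in the group to which they were randomized, and Section 4.1 randomizes within panels. If groups are panels or regimens, K and L simply yield a one-dose ratio at Day 85.
- A reader might infer that most of each group is single-dose. That is true of the whole set, but not within the 10^5 or 10^6 group.
- A reader might call footnote b a contradiction. In the text's model, group enters only through its interaction with time, so the footnote can be read as loose shorthand. It still needs tightening, because a group term without the interaction would not give a ratio for each visit.
- A reader might fault Table 10 for leaving Panel F without a post-dose-2 comparison. Section 3 leaves it out as well.

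**Conclusion.** The conflict between Table 10 and Section 3 stands and rests on the text alone. Table 10's Day 85 set includes 75 of 135 participants who have had only one dose, and the table omits the Day 197 ratio for K and L. Dilution is conditional. If groups are pooled by dose level, and under the assumed ratios in the working, a true 3.0 would appear as about 2.2 to 2.5. If groups are panels or regimens there is none, but F, K and L are still compared at a visit Section 3 does not name for them.

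The weight is moderate. The endpoint is secondary and Section 9.9.2 calls the study descriptive, with no hypotheses. Section 8.11.4 records termination, with a final visit at least 56 days after the last vaccination and no antibody serum taken at it, so Day 197 data may not exist. A reader might infer that termination makes the point moot. It does not: without Day 197 data, Day 85 would be the only post-dose-2 comparison left among those Section 3 names, and that is where the panel set is wrong. The documents do not say how much Day 85 data was collected.

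**What to change.** - Change the Table 10 ratio row to: Day 29 (all panels); Day 85 (Panels A, B, I, J); Day 197 (Panels K, L). Give the Day 197 entry its population and its primary or supportive role.
- Define vaccination group for the cLDA, and do not combine one-dose and two-dose participants in one group at visits after Day 57.
- Reword footnote b to match the Section 9.6.2 model: time, time-by-group and a common baseline.
- If termination leaves no Day 197 data, report that comparison as not estimable and do not substitute Day 85.
- The sponsor should state, in Section 3 and Table 10 alike, whether Panel F has a Day 197 comparison. Adding it to Table 10 alone would create a new mismatch.

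The cost is analysis-plan wording, plus a line in Section 3 for Panel F. No new data are needed. The change should be made before unblinding for the final analysis. Limiting Day 85 to A, B, I and J widens the interval as shown in the working; that is the precision the design gives for this comparison.
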